### [4] Follow-up surveillance

For a period of 3 years from the date of treatment start, follow-up surveillance for subjects in the Xeljanz group (1) and the control group will be conducted on the information related to the drug administration conditions and adverse events after discontinuation (serious infections [12 months], malignant tumors, adverse events leading to death).

Booklet No.	Observation period	Safety		Effectiveness		
		Xeljanz group	Control group	Xeljanz group	Control group	
Booklet 1 d)	Treatment start to Month 6 d)	All adverse events	Serious infection, Malignant tumor, Death	Before treatment start, At Month 6	-	
Booklet 2	Months 7 to 12			At Month 12		
Booklet 3	Months 13 to 24		Malignant tumor, Death	At Month 24		
Booklet 4	Months 25 to 36			At Month 36		
Follow-up survey form d)	Performed for 3 years from the start of treatment for subjects who prematurely discontinue treatment d)					

d) For subjects who correspond to “[1] Xeljanz group (2)”; the observation period will be only the duration of 6 months from the date of treatment start (Booklet 1) and no follow-up surveillance will be conducted.

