#### **4. HYPOTHESES AND DECISION RULES**

Since this survey is not a confirmatory study, statistical tests will be exploratory. Unless otherwise specified, tests will be 2-sided and the significance level will be 5%. A 2-sided confidence interval will be used for interval estimation, and the confidence coefficient will be 95%.

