## **6. ENDPOINTS AND COVARIATES**

### **6.1. Safety Endpoints**

#### **6.1.1. Comparison of Xeljanz group and control group**

- Malignant tumors are tumors with definitive diagnosis among all-causality malignant tumors (including lymphoma).
- Time to occurrence of malignant tumor
- Serious infections are infections corresponding to the following among all-causality infections.
  1. Results in death, or is life-threatening;

2. Results in disability, or may lead to disability;
  3. Requires inpatient hospitalization or prolongation of hospitalization;
  4. Are serious in accordance with the above.
- Time to occurrence of serious infection
  - Death refers to the case where the death column is checked in the status of treatment of Xeljanz (continued or discontinued) or the status of follow-up (continued or discontinued) in the case report form (CRF).

The death was defined to exclude post-survey deaths for comparing fairly in the Xeljanz and control groups, because post-survey deaths are likely to be collected only in the Xeljanz group. However, it was found that there were death cases that were possibly to have been confirmed at the end of the survey and had no reason for discontinuation of the treatment or the follow-up, when the final analysis for the reexamination application (cutoff data on 12/July/2021) was conducted. Since it was found that there were cases that were considered to be high, such cases were exceptionally regarded as cases where the investigation was discontinued due to patient death, and were included in the analysis as cases of death. Such cases were exceptionally regarded as death cases where the survey was discontinued due to death, and were included in the analysis as death cases. The handling of death cases is described in Section 7.

- Time to death

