### 8.1.6. Group Comparison of Incidence Rate and Incidence Proportion of Specified Events

Specified events including initial malignancy, initial severe infection, and death will be compared between groups in terms of the following quantities:

- **Incidence ratio between the treatment groups and the 95% confidence interval**

$$\text{Incidence ratio} = \frac{a/\text{PT}_1}{b/\text{PT}_0}$$

95% confidence interval for incidence ratio

$$= \exp \left[ \left\{ \ln \left( \frac{a/\text{PT}_1}{b/\text{PT}_0} \right) \pm 97.5 \text{ percentile for standard normal distribution} \times \sqrt{\frac{1}{a} + \frac{1}{b}} \right\} \right]$$

Xeljanz group a: Number of patients with the event [patient], PT1: Duration of exposure [patient-year]

Control group b: Number of patients with the event [patient], PT0: Duration of exposure [patient-year]

- **Difference in incidence rates between treatment groups and its 95% confidence interval**

Difference in incidence rates [patient/100 patient-years]

$$= 100 \times \left( \frac{a}{\text{PT}_1} - \frac{b}{\text{PT}_0} \right)$$

95% confidence interval for difference in incidence rates [patient/100 patient-years]

$$= 100 \times \left\{ \left( \frac{a}{PT_1} - \frac{b}{PT_0} \right) \pm 97.5 \text{ percentile for standard normal distribution} \right. \\ \left. \times \sqrt{\frac{a}{PT_1^2} + \frac{b}{PT_0^2}} \right\}$$

- **Ratio of incidence proportions between treatment groups and its 95% confidence interval**

$$\text{Ratio of Incidence proportions} = \frac{a/N_1}{b/N_0}$$

95% confidence interval for ratio of incidence proportions

$$= \exp \left[ \left\{ \ln \left( \frac{a/N_1}{b/N_0} \right) \pm 97.5 \text{ percentile for standard normal distribution} \right. \right. \\ \left. \left. \times \sqrt{\frac{1}{a/N_1} + \frac{1}{b/N_0}} \right\} \right]$$

Xeljanz group

$N_1$ : Number of patients included in the analysis [patient]

Control group

$N_0$ : Number of patients included in the analysis [patient]

- **Difference in incidence proportion between the treatment groups and the 95% confidence interval**

$$\text{Difference in incidence proportion [%]} = 100 \times \left( \frac{a}{N_1} - \frac{b}{N_0} \right)$$

95% confidence interval [%] for the difference in incidence proportion

$$= 100$$

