- **Distribution of propensity score and covariates before and after adjustment for hazard ratio of malignant tumor**

The distribution of propensity scores before and after adjustment by weighting of propensity scores is estimated using kernel density estimation and shown by violin plot. In the control group, a boxplot of weights is created.

In addition, the proportion of each category of patient background used for the covariate and the difference between the standardized groups are calculated before and after adjustment. The standardized difference is treated as a continuous amount in the patient background of 3 or more categories, and calculated by the difference / standard deviation of the average value of each group. In the patient background of the binary data, it is calculated by the difference / standard deviation of the ratio of each group. In addition, parameters are calculated in logistic regression model.

- **Standardized incidence rate (SIR) for the development of malignant tumors**

Using the number of malignant tumors in each group, the SIR and its 95% confidence interval with the Japanese as the reference population are calculated according to Section 8.1.6. The expected number of patients is calculated using the population and morbidity by gender and age in 2013.

In addition, the SIR and its 95% confidence interval calculated by using the population and the number of morbidity by gender, age, and calendar year as the expected number of patients are calculated according to Section 8.1.6. If there is no reference population and prevalence in the applicable calendar year, use the reference population and prevalence by gender and age in the latest year.

In addition, SIR is calculated for each cancer type (stomach, lung, breast, cervix, uterine body, ovary, malignant lymphoma, large intestine, pancreas, bladder, kidney / urinary tract (excluding bladder)). Females are targeted for malignant tumors of the breast, cervix, uterine body and ovaries.

Similarly, it is calculated for non MTX adherent safety analysis set.

The Cancer Information of the National Cancer Center Service is used as Japanese population data, and the expected number of patients is calculated using the population and the number of morbidity in the statistical data on cancer.

”.

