**Table 6. Definitions in the Comparison of Serious Infections**

Term	Definition
Patients without serious infections	Patients who do not correspond to the each definition of patients with serious infections
Time to serious infections during the treatment period (+28 days)	Date of the development of serious infections- date of the initiation of treatment + 1 Both treatment groups will be analyzed for the duration of treatment + 28 days (up to not longer than 1 years).
Censoring period for patients without serious infections during the treatment period (+28 days)	Date of the completion of treatment + 28- date of the initiation of treatment + 1 Both treatment groups will be analyzed for the duration of treatment + 28 days (up to not longer than 1 years).
Time to serious infection during treatment period	Date of the development of serious infection - date of the initiation of treatment + 1 The upper limit is 1 year (366)
Censoring period for patients without serious infections during treatment period	Date of the completion of treatment - date of the initiation of treatment + 1 The upper limit is 1 year (366)
Time to serious infection during overall observation period	Date of the development of serious infection - date of the initiation of treatment + 1 The upper limit is 1 year (366)
Censoring period for patients without serious infections during overall observation period	Date of completion or discontinuation of follow-up - date of the initiation of treatment + 1 The upper limit is 1 year (366)

- **Development of serious infections**

The number of serious infections in each group and the proportion of occurrence are calculated for each SOC and PT. Furthermore, it is calculated for each infection type.

- **Incidence rate of serious infections**

The number of patients with serious infections in each group, incidence rate, and the 95% confidence interval will be calculated in accordance with [Section 8.1.5](#).

In addition, the incidence ratio between treatment groups and the 95% confidence interval and the difference in incidence rate between treatment groups and the 95% confidence interval will be calculated.

The above analyses will be also conducted for serious infections excluding serious herpes zoster and for serious herpes zoster, respectively.

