For covariates concerning serious infections ([Section 6.3](#)), incidence by single factor will be calculated, and the pooled incidence ratio and the 95% confidence interval and the pooled difference in incidence rate and the 95% confidence interval will be calculated.

Incidence ratio with its 95% CI will be calculated for events of herpes zoster, opportunistic infection, and tuberculosis as well as “serious infections” .

- **Incidence proportion of serious infections**

The number of patients with serious infections in each group, the incidence proportion, and the 95% confidence interval will be calculated in accordance with [Section 8.1.5](#).

In addition, the ratio of incidence proportion and the 95% confidence interval and the difference in incidence proportion and the 95% confidence interval will be calculated.

The above analyses will be also conducted for serious infections excluding serious herpes zoster and for serious herpes zoster, respectively.

For covariates concerning serious infections ([Section 6.3](#)), the incidence proportion by single factor will be calculated, and the ratio of the pooled incidence proportion and the 95% confidence interval and the difference in the pooled incidence proportion and the 95% confidence interval will be calculated. Age will be handled as categorical data.

Incidence proportion with its 95% CI will be calculated for events of herpes zoster, opportunistic infection, and tuberculosis as well as “serious infections” .

- **Analysis of time to serious infection**

- Time to serious infection in each group will be summarized in accordance with [Section 8.1.4](#). As for the censoring period in patients without serious infection, [Table 5](#) will be followed. In addition, a graph showing the transition of the incidence rate estimated using the calculated parameters by applying the Weibull distribution together with the Kaplan-Meier plot, and a graph of the transition of the hazard function are created. **Adjusted hazard ratio for the development of serious infections**

As for time to serious infection, the adjusted hazard ratio of the Xeljanz group to the control group for the development of serious infections and the 95% confidence interval will be calculated in accordance with [Section 8.1.5](#). Covariates used for adjustment are shown in [Section 6.3](#).

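### SAP 8.2.3.1.2 does not limit the between-group ratio for opportunistic infection, herpes zoster and tuberculosis to serious events; as worded, the opportunistic infection ratio is biased upward (minor, exploratory).

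*SAP*

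**What the plan says.** SAP 8.2.3.1 is the comparison of the Xeljanz and control groups, and 8.2.3.1.2 is its part on serious infections. Under the incidence rate bullet the SAP states: "Incidence ratio with its 95% CI will be calculated for events of herpes zoster, opportunistic infection, and tuberculosis as well as" serious infections. The incidence proportion bullet has a parallel line: "Incidence proportion with its 95% CI will be calculated for events of herpes zoster, opportunistic infection, and tuberculosis as well as" serious infections. Neither line restricts the three named event types to serious cases. Earlier in the same bullets, the SAP already plans the rate, ratio and difference, and the proportion analyses, for herpes zoster explicitly qualified as serious.

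The surrounding definitions cover serious infection only. SAP 6.1.1 defines the comparative endpoint by four seriousness criteria: "Serious infections are infections corresponding to the following among all-causality infections". Table 6 gives event time, censoring and the one-year limit for serious infections: "Both treatment groups will be analyzed for the duration of treatment + 28 days (up to not longer than 1 years"). The ratio itself is the one in SAP 8.1.6, "Incidence ratio between the treatment groups and the 95% confidence interval".

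The protocol collects events differently in the two groups. In the booklet table of Protocol 6.5 [4], the Xeljanz group has all adverse events; the control group entry for the first booklet is "Serious infection, Malignant tumor, Death". Note *5 to the Protocol section 7 schedule confirms this and limits control reporting of serious infections to the first 12 months. Protocol 7.6 and 7.8 name herpes zoster and tuberculosis inside the control group's serious-infection item. Opportunistic infection is not named there.

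**The concern.** A ratio of incidence rates is interpretable only if both numerators count the same kind of event. Read literally, the Xeljanz numerator for opportunistic infection includes non-serious cases that control sites were never asked to report. Part or all of a raised ratio would then reflect reporting rules and could be mistaken for a drug effect, on a topic (infection compared with controls) that is a stated objective of the surveillance.

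The SAP deals with unequal collection elsewhere. SAP 6.1.1 excludes post-survey deaths because they are likely to be collected only in the Xeljanz group. It also adds an analysis restricted to case report form information, because information obtained after transfer is not collected for controls. The serious versus non-serious imbalance gets no such treatment. The form-only analysis does not remove it, because the Xeljanz survey form itself covers all adverse events.

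**Working it through.** **Reporting rules side by side**

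| Event type | Xeljanz group | Control group |
|---|---|---|
| Opportunistic infection | all cases | serious cases only, 12 months |
| Herpes zoster, tuberculosis | all cases | serious cases, 12 months; non-serious cases unclear |
| Serious infection | all cases | all cases, 12 months |

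**Size of the bias.** The documents give no rate or serious share for these events, so there is no plan figure to reproduce for them. SAP 8.1.6 uses ratio = (a/PT1)/(b/PT0), with 95% limits ratio × exp(±1.96 × √(1/a + 1/b)). Let r be the true rate of events of any seriousness, equal in both groups, and s the serious share. Expected counts as worded are a = r × PT1 and b = r × s × PT0, so

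expected ratio = r / (r × s) = 1/s.

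| s (assumed) | 20% | 50% | 70% | 90% | 100% |
|---|---|---|---|---|---|
| Ratio with no true difference | 5.0 | 2.0 | 1.4 | 1.1 | 1.0 |

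The factor is never below 1, so the direction is upward or nil.

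**Chance of a falsely raised interval.** Inputs from the protocol are group sizes of 4000 and 2000 (or 3000 and 2400, the last row of the Appendix table) and about 50% drop-out at 3 years. The assumptions are r, s and a constant drop-out hazard of ln 2/3 = 0.231 per year. Mean follow-up in year 1 is (1 − e^(−0.231))/0.231 = 0.893 years. Patient-years are therefore 3572 and 1786, or 2679 and 2143. With Poisson counts, enumerating every pair and treating zero counts as not excluding 1, the chance that the 8.1.6 interval lies wholly above 1 with no true difference, at s = 50%, is:

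| r per 100 patient-years (assumed) | 0.1 | 0.2 | 0.5 | 1 | 2 |
|---|---|---|---|---|---|
| 4000 vs 2000 | <0.01% | 0.1% | 16% | 46% | 79% |
| 3000 vs 2400 | 0.02% | 1.4% | 22% | 49% | 80% |

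At r = 1 and 4000 vs 2000 the chance falls to 17% at s = 70% and 4% at s = 90%.

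**Check on the drop-out assumption.** The protocol's 104 expected malignancies follow from linear drop-out: 4000 × (0.5 × 3 + 0.5 × 1.5) = 9000 patient-years, × 1.16/100 = 104.4. The constant hazard gives 100.4. Using linear drop-out here (0.917 years per patient in year 1) moves the 46% to 47%, and the 1/s factor does not depend on this choice.

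**With serious events only in both groups.** Expected counts become r × s × PT1 and r × s × PT0, and the expected ratio is 1.0 for any s that is equal in the two groups. At r = 1 per 100 patient-years and s = 50%, the chance of a falsely raised interval is 1.4% (4000 vs 2000) or 2.0% (3000 vs 2400).

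**The case against.** The strongest reply is that the lines were never meant to reach beyond serious events. The section title, the bullet titles, Table 6 and the 6.1.1 endpoint list all concern serious infections, and no non-serious infection endpoint exists in the comparison. SAP 8.2.3.2 also has a sentence treating the same three event types as part of the serious-infection category and then individually. This reading is available, and under it there is no bias. It is not stated, however. The 8.2.3.2 sentence is garbled and belongs to the Xeljanz-only analysis. If herpes zoster here meant serious herpes zoster, the line would repeat a ratio already planned in the same bullet. That contrast is suggestive and not decisive, because the line also repeats the serious-infection ratio.

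A second reply is that ratio is a slip for rate, perhaps in a line intended for the Xeljanz group alone, since no control group is named. The SAP does mix the two words: its SIR is a ratio in 8.1.6 but appears as "Standardized incidence rate (SIR) for the development of malignant tumors" in 8.2.3.1.1. The matching proportion line also promises no ratio. A slip is possible, but the section is comparative, and rates shown side by side would carry the same imbalance. Only a Xeljanz-only line would avoid it, and the text does not say that.

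A third reply is that both the serious share and the event rate are assumed, so the size is unknown. This stands. The false-high chance runs from below 0.01% to 80% in the tables above, and a serious share near 100% leaves almost no bias. The direction does not depend on these assumptions.

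Finally, SAP section 4 states: "Since this survey is not a confirmatory study, statistical tests will be exploratory". This also stands, and it sets the severity.

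**Conclusion.** The concern holds as a minor one. Followed as worded, the opportunistic infection ratio compares events of any seriousness with serious events and is inflated by 1/s: 2.0 at an assumed serious share of 50%, 1.1 at 90%, and nil at 100%. This rests on three conditions: the literal wording is applied, a between-group comparison is meant, and some opportunistic infections are non-serious. For herpes zoster and tuberculosis no bias is asserted. It is nil if all such cases were reportable in controls, and the same 1/s if only serious ones were.

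The affected output is unadjusted, supplementary and exploratory. The primary serious-infection comparison, its adjusted and propensity-weighted hazard ratios, and the separate serious herpes zoster ratio are unaffected.

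**What to change.** In both sentences of SAP 8.2.3.1.2, limit the between-group ratio (or rates) and the proportions for the three event types to events meeting the 6.1.1 seriousness criteria in both groups, within the one-year window of Table 6. If ratio was meant as rate, correct the word. Report events of any seriousness for the Xeljanz group only, in 8.2.3.2, which already tabulates these event types individually. State whether non-serious herpes zoster and tuberculosis were collected in controls.

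The cost is a wording change in two sentences and somewhat wider intervals. At an assumed 1 per 100 patient-years and s = 50%, with 4000 vs 2000 patients, expected events go from 36 vs 9 to 18 vs 9. The 95% limits move from the ratio multiplied or divided by exp(1.96 × √(1/35.7 + 1/8.9)) = 2.08 to exp(1.96 × √(1/17.9 + 1/8.9)) = 2.23.

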\*5: All adverse events in the Xeljanz group are subject to reporting.

In the control group, the following adverse events are subject to reporting.

- Serious infections: For 12 months from the start of surveillance

- Malignant tumor and adverse events leading to death: For 36 months from the start of surveillance

\*6: For patients in the Xeljanz group (“1) Xeljanz group (2) in 6.5 observation period”) after the registration of patients in the control group is completed; only information until 6 months after the start of surveillance (Booklet 1) should be collected and no follow-up surveillance will be conducted.

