## **2.2. Study Objectives**

*This survey will be performed in patients administered Xeljanz Tablets (hereinafter referred to as Xeljanz) to obtain information on the following under the actual use conditions after marketing:*

- 1) *Development of adverse drug reactions, factors that may affect safety, and efficacy*
- 2) *Safety (malignant tumors and serious infections in particular) and efficacy in long-term use*

*The development of malignant tumors and serious infections will be compared with the control group.*

Since it has been suggested in Japanese clinical trials that Xeljanz may promote the manifestation of malignant tumors, the development of malignant tumors in the Xeljanz group will be compared with that in the control group by 3-year observation. The development of serious infections in the Xeljanz group will be compared with that in the control group by 1-year observation.

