**Table 1. Other Interim Analyses**

	Objective	Timing of implementation	Target patients
2	Safety evaluation of Xeljanz Safety evaluation of control group	The timing at which 6-month data of about 1000 patients in Xeljanz group are fixed.*	Xeljanz group: Patients for whom at least Volume 1 is fixed at the specified timing. Control group: patients for whom at least Volume 1 is fixed at that timing.
3	Safety evaluation of Xeljanz Safety evaluation of control group	The timing at which 6-month data of about 2000 patients in Xeljanz group are fixed.*	Xeljanz group: Patients for whom at least Volume 1 is fixed at the specified timing. Control group: patients for whom at least Volume 1 is fixed at that timing.
4	Safety evaluation of Xeljanz intended to discharge the all-cases survey.	The timing at which 6-month data in 4000 patients in the Xeljanz group are fixed.	Xeljanz group: Patients for whom at least Volume 1 is fixed at the specified timing. Control group: patients for whom at least Volume 1 is fixed at that timing.
5	Comparison of serious infection with control group	The timing at which 1-year data in all patients in Xeljanz group and control group are fixed.	All cases of Xeljanz and Control groups

\* The time of implementation will be decided based on the number of collected cases and duration.

At interim analyses, only the analyses of necessary items among statistical analyses specified in this plan will be performed. Items necessary for the interim analysis will be specified separately. At the final analysis, all analyses specified in this plan will be performed.

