#### **8.2.3.1.1. Analysis of malignant tumors**

There are the following 3 definitions for patients with malignant tumors, and the analysis will be performed for each of them. As the primary evaluation, patients with malignant tumors during overall observation period will be used. For other definitions, the incidence of malignant tumor will be calculated, and other relevant analyses will be performed if such result is remarkably different from the data on overall observation period.

- Patients with malignant tumors during overall observation period: Patients with malignant tumors during overall observation period are patients in whom malignant tumors developed from the date of the initiation of treatment to the date of the completion or discontinuation of follow-up.
- Patients with malignant tumors during treatment period: Patients with malignant tumors during treatment period are patients in whom malignant tumors developed from the date of the initiation of treatment to the date of the completion of treatment.
- Patients with malignant tumors during treatment period+28 days: Treatment period will cover 28 days following the completion of treatment; that is, patients to be included in the analysis will be those with malignant tumors developed from the date of the initiation of treatment + 28 days (or not longer than 3 years if the treatment period + 28 days exceeds 3 years).

Other definitions used in the comparison of malignant tumors are shown in [Table 5](#).

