**Table 5. Definitions in the Comparison of Malignant Tumors**

Term	Definition
Patients without malignant tumors	Patients who do not correspond to the each definition of patients with malignant tumors
Time to malignant tumor during overall observation period	Date of the development of malignant tumor - date of the initiation of treatment + 1
Censoring period for patients without malignant tumors during overall observation period	Date of completion or discontinuation of follow-up - date of the initiation of treatment + 1
Time to malignant tumor during treatment period	Date of the development of malignant tumor - date of the initiation of treatment + 1
Censoring period for patients without malignant tumors (treatment period)	Date of the completion of treatment - date of the initiation of treatment+ 1
Time to malignant tumor during the treatment period (+28 days)	Date of the development of malignant tumor - date of the initiation of treatment + 1
Censoring period for patients without malignant tumors during the treatment period (+28 days)	Date of the completion of treatment + 28- date of the initiation of treatment + 1

• **Development of malignant tumors**

The number of malignant tumors in each group and the proportion of occurrence are calculated for each SOC and PT. Furthermore, it is calculated for each cancer type (stomach, lung, breast, cervix, uterine body, ovary, malignant lymphoma, large intestine, pancreas, bladder, kidney / urinary tract (excluding bladder), other). Females are targeted for malignant tumors of the breast, cervix, uterine body and ovaries.

• **Incidence rate of malignant tumors**

The number of patients with malignant tumors in each group, incidence rate, and the 95% confidence interval will be calculated in accordance with [Section 8.1.5](#).

In addition, the incidence ratio between treatment groups and the 95% confidence interval and the difference in incidence rate between treatment groups and the 95% confidence interval will be calculated.

For covariates concerning malignant tumors (Section 6.3), incidence by single factor will be calculated, and the pooled incidence ratio and the 95% confidence interval and the pooled difference in incidence rate and the 95% confidence interval will be calculated.

• **Incidence proportion of malignant tumors**

The number of patients with malignant tumors in each group, the incidence proportion, and the 95% confidence interval will be calculated in accordance with [Section 8.1.5](#).

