#### **8.2.3.1.2. Analysis of serious infections**

There are the following 3 definitions for patients with serious infections, and the analysis will be performed for each of them. As the primary evaluation, patients with serious infections during treatment period + 28 days will be used. For other definitions, the incidence of serious infections will be calculated, and other relevant analyses will be performed if such result is remarkably different from the data on treatment period + 28 days.

- Patients with serious infections during treatment period +28 days: Patients with onset of serious infections during the treatment period (+28 days): Treatment period will cover 28 days following the completion of treatment; that is, patients to be included in the analysis will be those with onset of serious infections developed from the date of the initiation of treatment + 28 days.
- Patients with serious infections during treatment period: patients with serious infections during treatment period are patients in whom serious infections developed from the date of the initiation of treatment to 1-year later (Day 366) or the date of the completion of treatment, whichever comes first.
- Patients with serious infections during overall observation period (up to 1 year): patients with serious infections during overall observation period (up to 1 year) are patients in whom serious infections developed from the date of the initiation of treatment to the date of the completion or discontinuation of follow-up.

Other definitions used in the comparison of serious infections are shown in Table 6.

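### The time-to-serious-infection analysis points to the malignant-tumor censoring table (Table 5, no 1-year limit) instead of Table 6; followed literally, the control Weibull and hazard plots would show a falsely falling risk

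*SAP*

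**What the plan says.** SAP section 8.2.3.1.2, under the analysis of time to serious infection, asks for a Kaplan-Meier summary, a Weibull curve drawn with the Kaplan-Meier plot, and a graph of the hazard function. For event-free patients it says: "As for the censoring period in patients without serious infection, [Table 5](#) will be followed".

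Table 5 belongs to the other endpoint. SAP section 8.2.3.1.1 introduces it with "Other definitions used in the comparison of malignant tumors are shown in [Table 5". Its censoring row for treatment + 28 days reads "Date of the completion of treatment + 28- date of the initiation of treatment + 1", and no row has a 1-year limit. The only limit nearby is 3 years, in the text definition for malignant tumors.

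Section 8.2.3.1.2 itself says: "Other definitions used in the comparison of serious infections are shown in Table 6". In Table 6 every time and censoring row is limited to 1 year. For the primary definition the wording is "Both treatment groups will be analyzed for the duration of treatment + 28 days (up to not longer than 1 years".

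The 1-year horizon is part of the design. SAP section 2.2 says: "The development of serious infections in the Xeljanz group will be compared with that in the control group by 1-year observation". For controls, Protocol section 7 (footnote 5) limits reporting: "Serious infections: For 12 months from the start of surveillance". Protocol section 6.5 nevertheless observes controls for 36 months. The same footnote has the Xeljanz group report all adverse events.

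**The concern.** The SAP gives two different censoring rules for one analysis. The malignancy and death sections each cite their own table (Tables 5 and 7). Only the infection section cites another endpoint's table, which looks like a sentence carried over from section 8.2.3.1.1.

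The difference matters because a Weibull fit uses all the person-time it is given. If infections stop being collected at 12 months but infection-free controls stay at risk until as late as 3 years, the model reads the later years as truly infection-free and bends the hazard downwards to match. The hazard graph is where a reader looks to see whether infection risk changes over time. It would show an early peak and a decline even if the risk were flat. The problem would arise mainly at the final analysis, when long follow-up is available and the SAP (section 3) says: "At the final analysis, all analyses specified in this plan will be performed".

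**Working it through.** **Inputs from the documents.** Event and censoring limit under Table 6: Day 366. Longest follow-up: 3 years. Dropout at 3 years: about 50% (Protocol section 3).

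**Assumed inputs.** The documents give no serious-infection rate. The base case is a constant 3 per 100 patient-years, with 2 to 5 per 100 and 30% to 70% dropout as the range.

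**Dropout pattern.** Linear dropout reproduces the plan's one computed figure, the 104 expected malignancies: 4000 × 3 × (1 + 0.5)/2 = 9000 patient-years, and 9000 × 1.16/100 = 104.4. Exponential dropout gives 100.4. Linear dropout is therefore used.

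**Method.** The Weibull shape k solves

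Σ tᵏ ln t / Σ tᵏ − 1/k = mean of ln t among events,

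with the sums over all patients. Lengthening only the censored times raises the first term and leaves the right-hand side alone, so k must fall.

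**Hand check (rare events, no dropout).** With a constant hazard, event times are roughly uniform over year 1, so the mean of ln t is about −1.
- Everyone censored at 1 year: ln 1 = 0, so 1/k = 1 and k = 1.
- Everyone censored at 3 years: ln 3 = 1.10, so 1/k = 2.10 and k = 0.48.

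**Base-case fit.** Treatment end + 28 days, at most 3 years; events limited to Day 366 under both tables, and only the censoring differs:

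| Quantity | Table 6 | Table 5 |
|---|---|---|
| Person-time after Day 366 | none | 59% |
| Weibull shape | 1.00 | 0.53 |
| Fitted 1-year incidence | 2.97% | 1.85% |
| Fitted hazard at month 12, per 100 patient-years | 3.01 | 0.99 |

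The exact 1-year incidence is 1 − exp(−0.03 × 366/365.25) = 2.96%. Repeat fits gave 2.94% to 2.98% under Table 6 and 1.84% to 1.85% under Table 5. The incidence is understated by 1 − 1.85/2.97 = 38%, and the month-12 hazard by 1 − 0.99/3.01 = 67%. From month 1 to month 12 the fitted hazard falls by a factor of 12^(1 − 0.53) = 3.2, although the true hazard is flat.

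**Range.** Over 2 to 5 per 100 patient-years and 30% to 70% dropout, the shape is 0.51 to 0.56, the 1-year incidence is 36% to 39% too low, and the month-12 hazard is 64% to 69% too low. With exponential dropout of 30% to 50% and rates of 1 to 10 per 100, the shape is 0.51 to 0.55. A truly rising risk (shape 1.2) is fitted as 0.58.

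**Xeljanz group.** If its event times keep the 1-year limit of Table 6, the distortion is the same. If Table 5 also governed its event times, a constant Xeljanz hazard would be fitted with shape 1.00. Only the control curve would then fall falsely.

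**Kaplan-Meier and Cox.** With events limited to Day 366, the set of patients at risk at each event time is the same under both tables. In a simulated comparison of 4000 with 2000 patients, the hazard ratio (1.246) and survival at Day 366 (0.9366) were identical.

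**Incidence rate.** SAP section 8.1.5 builds exposure from times to event and to censoring. If the Table 5 times were reused there, the base-case rate of 3.0 would become 3.0 × (1 − 0.59) = 1.2 per 100 patient-years. In the simulated comparison the ratio between groups barely moved (1.246 to 1.236).

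**The case against.** The strongest reply is that this is a visible cross-reference slip that nobody would program. Table 5 has no row for patients without serious infection, so it cannot be applied without substituting the event. Table 6 has matching rows, is named in the same section, and states a limit for the whole analysis. SAP section 2.2 fixes a 1-year comparison. The same section has a similar slip: it sends the adjusted hazard ratio to section 8.1.5, although the Cox model is described in 8.1.6. The misfit would also show, because the Weibull curve is drawn with the Kaplan-Meier plot, and 1.85% would sit beside about 2.97% at 1 year.

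Most of this stands. The intent is clear and a careful programmer may well use Table 6. It lowers the likelihood and the severity. It does not remove the contradiction, because the sentence that names Table 5 is the specific instruction for this analysis.

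Three stronger readings are tempting, and the documents do not support them:
- **Both groups' curves would certainly be wrong.** Only control-group collection stops at 12 months. For Xeljanz the distortion depends on which rule governs its event times.
- **The group comparison is biased.** With events limited to 1 year, the Cox hazard ratio does not change.
- **The incidence rates are wrong, or are certainly safe.** Neither follows. The sentence concerns the time-to-event analysis, and the SAP does not say whether section 8.1.5 would share its times.

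**Conclusion.** The cross-reference is wrong as written and conflicts with Table 6, the 1-year comparison and the 12-month collection in controls. If it is followed, the control Kaplan-Meier plot gains a false flat tail after month 12, and the control Weibull curve and hazard plot show a falling risk even when the true risk is constant.

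The numerical size rests on an assumed infection rate and dropout pattern, but the shape hardly depends on either. The harm is conditional on literal programming and falls on descriptive outputs in a survey whose tests the SAP (section 4) calls exploratory. Severity is minor.

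**What to change.** In SAP section 8.2.3.1.2, in the sentence on the censoring period for time to serious infection, change Table 5 to Table 6. Nothing else is needed for this point, because Table 6 already carries the 1-year limit for event and censoring times in both groups.

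The cost is one digit and no new data. If any serious-infection Kaplan-Meier, Weibull or hazard plots were already drawn with Table 5 times, they need one rerun. It is also worth confirming that the section 8.1.5 incidence rates used Table 6 times.
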